²³ For female patients of childbearing potential only; pregnancy testing (serum hCG or high sensitivity urine) is required prior to dosing on Day 1 of Cycles ≥ 2 and at the EoBT Visit or within 3 days before the first dose of open-label selinexor (serum hCG). A positive urine pregnancy test will be confirmed by a serum pregnancy test. Test sensitivity for hCG must be ≥ 25 mIU/mL.

Table 2: Schedule of Assessments and Study Activities: Open-Label Selinexor

- EoBT Visit serves as baseline of Open-Label Selinexor; The EoBT Visit may occur at open-label (OL)-C1 D1 visit but must be \leq 14 days of last blinded dose. OL C1 D1 must occur within 14 days of the EoBT Visit.
- Patients in the selinexor arm who continue selinexor but as open-label treatment must complete the EoBT Visit before their next scheduled selinexor dose to maintain continuity of selinexor dosing from blinded to open-label treatment.
- Physical examination assessments and laboratory assessments done at the EoBT Visit do not need to be repeated at OL-C1 D1.

| | Open-Label Cycle 1 (42 days/6 wks) per cycle) | | Open-Label Cycle 2 | | Open-Label Cycle \geq 3 | End of Treatment (EoT) Visit | Safety Follow- up Call ¹⁵ | Survival Follow-up ¹⁶ |
|---|--|-----------------------------|-----------------------|-------------------------------------|------------------------------|------------------------------------|---|-------------------------------------|
| Schedule of Visit | Days 1, 8*, 15*, 22, 29* and 36* | Day 3 only ¹⁷ | Days 1, 15 and 29* | Days 10, 24 and 38 ¹⁷ | Days 1 and 22 | \leq 14 days Post- Last Dose | 30 days after last dose | Every 3 months |
| Visit window [±days] | ±1 day | + 1 day | ± 2 days | + 1 day | ± 2 days | | +7 days | ±14 days |
| Visit number | OL1-6 | Phone | OL7-9 | Phone | OL \geq 10 | In Office | Phone | Phone |
| Open-label informed consent ¹ | X (if not obtained at EoBT Visit) | | | | | | | |
| Clinical Assessments (if performed at EoBT, do not repeat at C1 D1) | | | | | | | | |
| Physical examination and vital signs (blood pressure, pulse, temperature) ² | X | | X | | X | X | | |
| Weight (indoor clothing without shoes) | X | | X | | X | X | | |
| Height (without shoes) | | | X (D1 only) | | X (D1 only) | X | | |
| BSA ³ | | | X (D1 only) | | X (D1 only) | X | | |
| ECOG | X (D1 only) | | X (D1 only) | | X (D1 only) | X | | |
| 12-lead ECG ⁴ | X (D1 only) | | | | | X | | |

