9.1.6. End of Blinded Treatment Visit; Return to the Clinic

At the time a patient permanently discontinues blinded study treatment or has PD prior to unblinding of all patients at the end of Phase 3 (ie, when the required number of PFS events for the primary PFS analysis are observed), a visit should be scheduled as soon as possible (within 14 days), at which time all of the assessments listed for the End of Blinded Treatment (EoBT) Visit will be performed. Study procedures will be performed ≤ 14 days after the last dose of study treatment, as specified in Table 1. An EoBT CRF page will be completed, giving the date and reason for stopping the study treatment. Patients lost to follow-up should be recorded as such on the appropriate eCRF.

For patients proceeding to open-label selinexor, the EoBT Visit will serve as the baseline for the open-label treatment phase. After the unblinding following the PFS analyses, patients in the selinexor arm who are continuing on selinexor but as open-label treatment must complete their EoBT Visit before their next scheduled selinexor dose.

- Informed consent for open-label selinexor (only for patients proceeding to open-label selinexor) and Assent Form for adolescent patients (permitted only in countries in

which adolescents have been approved by the national/local regulatory/ethical authority)

- Physical examination and vital signs (blood pressure, pulse, and body temperature) (Section 10.6.1.1)
- Weight, height, and BSA (Section 10.6.1.2)
- ECOG performance status assessment (Section 10.6.1.3)
- 12-lead ECG (Section 10.6.1.4)
- Urinalysis (Section 10.6.2.1)
- Hematology (Section 10.6.2.1)
- Complete serum chemistry (Section 10.6.2.1)
- Coagulation tests (Section 10.6.2.1)
- Serum hCG pregnancy test (females of childbearing potential only). Females of childbearing potential who are proceeding to open-label selinexor must have a negative serum hCG pregnancy test at the EoBT Visit (or within 3 days before the first dose of open-label selinexor). (Section 10.6.2.2)

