9.2. Description of Study Days: Open-label Selinexor

Please note:

- EoBT Visit serves as baseline of Open-Label Selinexor; The EoBT Visit may occur on the day of the patient's first open-label dose (OL-C1 D1 Visit) but must be ≤ 14 days of last blinded dose. OL C1 D1 must occur within 14 days of the EoBT Visit.
- Patients in the selinexor arm who continue selinexor but as open-label treatment must complete the EoBT Visit before their next scheduled selinexor dose to maintain continuity of selinexor dosing from blinded to open-label treatment.
- Physical examination assessments and laboratory assessments done at the EoBT Visit do not need to be repeated at OL C1 D1.

9.2.1. Visits OL1-6 (Cycle 1: Days 1, 8*, 15*, 22, 29*, and 36* [± 1 days]); Return to the Clinic

There are six clinic visits (ie, Days 1, 8*, 15*, 22, 29*, and 36*) during the first six-week cycle (Cycle 1).

Visits (ie, Days 8, 15*, 29*, and 36*) are not required for patients who continue selinexor but as open-label treatment.

The following study assessments will be performed during Cycle 1, as specified in [Table 2](#).

- Physical examination and vital signs (blood pressure, pulse, and body temperature) (Days 8*, 15*, 22, 29*, and 36*) [Section 10.6.1.1](#)
- Weight (Days 8*, 15*, 22, 29*, and 36*) ([Section 10.6.1.2](#))
- Limited serum chemistry (Days 8*, 15*, 22, 29* and 36*) ([Section 10.6.2.1](#))
- Tumor biopsy, only for patients who cross over from blinded placebo to open-label selinexor and have sufficient material available from a biopsy sample obtained during blinded study treatment (pre- or post-dosing) within 12 months prior to the first dose of open-label selinexor (Day 22 only). Note: If the biopsy is not performed on Cycle 1 Day 22, it may be performed on Cycle 2 Day 1 (see [Section 9.2.2](#)). Patients in the selinexor arm who continue on selinexor but as open-label treatment are not required to have an additional tumor biopsy on Cycle 1 Day 22 of open-label treatment. See [Section 10.11.3](#) for biopsy details.
- CCI
- CCI
- Nutritional consultation (should occur on Day 1 before the first dose of open-label selinexor) for patients in the placebo arm who cross over to open-label selinexor. The nutritional consultation is not required at C1 D1 of open-label selinexor treatment for patients in the selinexor arm who continue on selinexor but as open-label treatment. See [Section 10.7.3](#).
- Selinexor: in clinic dosing and dispensing of for home use

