- AEs and SAEs (throughout the cycle)
- Concomitant medications (throughout the cycle)

The following OL1 Visit (C1 D1) assessments will be performed only if they were not performed at the EoBT Visit:

- Informed consent for open-label selinexor and Assent Form for adolescent patients (permitted only in countries in which adolescents have been approved by the national/local regulatory/ethical authority) must be signed on or before the OL1 Visit

before any study-specific procedures for treatment with open-label selinexor are conducted at the OL1 Visit (Day 1 only)

- Physical examination and vital signs (blood pressure, pulse, and body temperature) (Day 1) Section [10.6.1.1](#))
- Weight (Day 1) (Section [10.6.1.2](#))
- ECOG performance status assessment (Day 1 only) (Section [10.6.1.3](#))
- 12-lead ECG (Day 1 only) (Section [10.6.1.4](#))
- Urinalysis (Day 1 only) (Section [10.6.2.1](#))
- Hematology (Day 1 only) (Section [10.6.2.1](#))
- Complete serum chemistry (Day 1 only) (Section [10.6.2.1](#))
- Coagulation tests (Day 1 only) (Section [10.6.2.1](#))
- QoL questionnaires (EORTC QLQ-C30 and EuroQoL EQ-5D-5L); Day 1 only, predose) (Section [10.7.1](#))

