2.6. BASELINE MEASUREMENT

For blinded treatment period, the baseline value is defined as the latest value prior to the first dose of blinded study treatment. In the case an assessment performed on the same date as the first dosing date, but it is impossible to determine the evaluation time relative to the time of taking the first dose, the evaluation time will be assumed to be following the protocol-defined schedule.

For patients who proceed to open-label period, the baseline value for assessments in open-label treatment period will be the latest value prior to the date of first open-label study treatment.

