2.7. VISIT WINDOWS

For safety data that are summarized/Plotted by time points, non-missing assessments from all scheduled and unscheduled visits will be mapped to an appropriate analysis visit using a windowing scheme. Analysis visit windows are defined in Table 2-1 to Table 2-2. If there are 2 or more assessments mapped to the same analysis visit for a patient, the assessment that is closest to the target visit day will be used for analysis. If there are 2 or more assessments mapped to the same analysis visit with the same distance from the target visit day, then select the latest one for the analysis.

Table 2-1 Visit Windows for Clinical Laboratory Tests for Patients in Blinded Treatment

Analysis Visit Name	Target Visit Day	Study Day Range in Window
Baseline	Day 1	Prior to or on Day 1
Day 43	Day 43	Day 2 to 64
Day 85	Day 85	Day 65 to 106
Day 127	Day 127	Day 107 to 148
Day 169	Day 169	Day 149 to 190
...		
(every 42 days)		

NOTE: Day 1 is the start date of blinded treatment period. The visit window is Target Date – 20 days to Target Date + 21 days for post-baseline visits, except Day 43 analysis visit.

Analysis visit and visit window may change for certain parameters depending on the data availability.

Table 2-2 Visit Windows for Clinical Laboratory Tests for Patients Who Enter Open-Label Treatment

Analysis Visit Name	Target Visit Day	Study Day Range in Window
OL Baseline	OL Day 1	Prior to or on OL Day 1
OL Day 43	OL Day 43	OL Day 2 to 64
OL Day 85	OL Day 85	OL Day 65 to 106
OL Day 127	OL Day 127	OL Day 107 to 148
OL Day 169	OL Day 169	OL Day 149 to 190
...		
(every 42 days)		

NOTE: Day 1 is the start date of open-label treatment period. The visit window is Target Date – 20 days to Target Date + 21 days for post-baseline visits, except OL Day 43 analysis visit. Analysis visit and visit window may change for certain parameters depending on the data availability.

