4.2.2.2. QLQ-C30

QLQ-C30 contains 30 questions and includes five functional scales (Physical, Role, Emotional, Social, and Cognitive Functioning), three symptom scales (Fatigue, Nausea/Vomiting and Pain) and a Global Health Status/QoL scale, and six single-item symptom items (dyspnoea, insomnia, appetite loss, constipation, diarrhoea and financial difficulties). The principle for scoring these scales is the same: 1. Calculate the mean of the items that contribute to the scale; this is the raw score. 2. Use a linear transformation to standardise the raw score, so that scores range from 0 to 100.

For functional scales and the global health status/QoL, a higher score represents a better level of functioning (better health status); for symptom scales/items, a higher score represents a higher level of symptomatology/problems (worse health status).

The missing data will be handled based on EORTC QLQ-C30 scoring manual (Fayers et al., 2001). The raw score (mean of the items that contribute to the scale) will only be calculated if at least half of the items (i.e., 3 of 6 items, or 3 of 5 items) from the domain have been answered. As a result, none of the single-item measures will be imputed.

The actual value and change from baseline before initiating a new antineoplastic treatment will be summarized using descriptive statistics over time for each of the five functional scales, three symptom scales and six items, and the global health status/QoL scale.

QLQ-C30 analyses will be summarized by treatment arm among Ph3-ITT, Ph3-PP, and Ph2-ITT populations. For exploratory purpose, QLQ-C30 will also be summarized in Ph3-OL and Ph2-OL populations, in which changes from baseline will be calculated using baseline values for the open-label period, i.e., last assessment on or before the start of open-label treatment.

Table 4-2 Scoring the QLQ-C30 version 3.0

	Scale	Number of items	Item range*	Version 3.0 Item numbers	Function scales
Global health status / QoL					
Global health status/QoL (revised) [†]	QL2	2	6	29, 30	
Functional scales					
Physical functioning (revised) [†]	PF2	5	3	1 to 5	F
Role functioning (revised) [†]	RF2	2	3	6, 7	F
Emotional functioning	EF	4	3	21 to 24	F
Cognitive functioning	CF	2	3	20, 25	F
Social functioning	SF	2	3	26, 27	F
Symptom scales / items					
Fatigue	FA	3	3	10, 12, 18	
Nausea and vomiting	NV	2	3	14, 15	
Pain	PA	2	3	9, 19	
Dyspnoea	DY	1	3	8	
Insomnia	SL	1	3	11	
Appetite loss	AP	1	3	13	
Constipation	CO	1	3	16	
Diarrhoea	DI	1	3	17	

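### The open-label baseline rule in SAP 2.6 excludes values taken on the first open-label dosing day, in conflict with the rest of the SAP and with a baseline visit that the protocol allows on that day

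*SAP*

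**What the plan says.** SAP 2.6 gives two baseline rules. For the blinded period, "the baseline value is defined as the latest value prior to the first dose of blinded study treatment", and a same-day assessment whose time relative to the dose cannot be determined is assumed to have followed the protocol schedule. For the open-label period, "the baseline value for assessments in open-label treatment period will be the latest value prior to the date of first open-label study treatment". The second rule turns on the date, not the dose, and has no same-day provision.

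Other parts of the SAP differ. Table 2-2 (SAP 2.7) gives the open-label baseline window for laboratory tests as "Prior to or on OL Day 1", with the first post-baseline window opening on OL Day 2. For QLQ-C30, SAP 4.2.2.2 takes the "last assessment on or before the start of open-label treatment", and SAP 4.2.2.3 does the same for EQ-5D-5L. SAP 5 describes the safety baseline as the last value before the first dose, then refers to 2.6 for details.

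In the protocol, section 9.1.6 states that for patients going on to open-label selinexor "the EoBT Visit will serve as the baseline for the open-label treatment phase". The notes to protocol Table 2 add: "EoBT Visit serves as baseline of Open-Label Selinexor; The EoBT Visit may occur at open-label (OL)-C1 D1 visit". Section 9.2 also lets the EoBT Visit come earlier, with the first open-label dose within 14 days after it. Section 9.2.1 lists OL Day 1 examination, weight, ECOG, ECG, laboratory and quality-of-life measurements, and says these "assessments will be performed only if they were not performed at the EoBT Visit".

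**The concern.** A patient whose EoBT Visit falls on OL Day 1 has a proper pre-selinexor baseline, taken when the protocol allows. The literal rule in SAP 2.6 discards it and reaches back to an earlier blinded visit.

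SAP 2.4 adds a second effect. For placebo crossovers, the blinded period stops short of the first open-label dosing date and the open-label period begins on it. By date, then, the discarded value belongs to the open-label period. It could be picked up as an on-treatment value in any worst, highest or last-value summary made for the open-label populations. Findings present before any selinexor, including changes that accompany progression, could then appear as changes on selinexor.

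The SAP does not say which of its baseline rules prevails, so two programmers could produce different tables from it.

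**Working it through.** The plan states no figure here to reproduce. The check sets the rules side by side and then works out visit days.

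**1. Does an OL Day 1 value taken before dosing count as open-label baseline?**

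| Place | Answer |
|---|---|
| SAP 2.6, open-label rule | No |
| SAP 2.7, Table 2-2 (laboratory) | Yes |
| SAP 4.2.2.2 and 4.2.2.3 (quality of life) | Yes |
| SAP 5 (safety) | Yes by its own words, but it refers to 2.6 |
| Protocol 9.1.6, 9.2 and Table 2 notes | Yes, if the EoBT Visit is that day |

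**2. Which items are exposed?** Quality of life has its own rule, and laboratory data summarised by time point have Table 2-2. Vital signs, weight, ECOG and ECG have no separate open-label baseline rule. Laboratory worst-grade and shift tables (SAP 5.3.2) are unclear, because the windows in SAP 2.7 are for data presented by time point.

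**3. Which patients?** The open-label populations contain only patients randomised to placebo who took open-label selinexor (SAP 3.1.3). The ceiling is the placebo arms: 30 in Phase 2 (protocol synopsis) and about 285/3 = 95 in Phase 3 (285 randomised per SAP 1.1, assuming the 2:1 ratio held). Neither the number who crossed over nor the share with EoBT on OL Day 1 is given.

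**4. How old would the baseline be?** Cycles last 42 days, so Day 1 of cycle k is study day 42 × (k − 1) + 1. This gives Day 43 for Cycle 2, Day 85 for Cycle 3 (week-12 scan) and Day 169 for Cycle 5 (week-24 scan).

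ECG: protocol Table 1 schedules blinded ECGs at screening, Cycle 1 Day 1, Cycle 2 Day 1 and EoBT. If EoBT is on OL Day 1 and is excluded, the last scheduled ECG is Day 43. Assume OL Day 1 is 0 to 14 days after the scan that shows progression, and no unscheduled ECG.

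- Week 12: 85 − 43 = 42 to 99 − 43 = 56 days.
- Week 24: 169 − 43 = 126 to 183 − 43 = 140 days.

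A longer wait for the central reading would add to these ages.

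Other items, Cycle 3 onward: the last dosing day in a cycle is Day 38, and EoBT may follow the last blinded dose by up to 14 days.

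- Measured on Day 1 only (such as ECOG): at most 38 + 14 − 1 = 51 days.
- Measured on Days 1 and 22 (vital signs, weight): at most 38 + 14 − 22 = 30 days. With the last dose on Day 17, before the Day 22 visit, the result is the same: 17 + 14 − 1 = 30.

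These use scheduled days and ignore visit windows.

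**5. What enters the open-label period?** The only scheduled open-label ECGs are OL Day 1 (if not done at EoBT) and End of Treatment. With EoBT on OL Day 1, the ECG taken that day would be one of only two scheduled ECGs dated within the open-label period, and it would not be baseline. SAP 5.5 compares baseline with the highest later ECG value.

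**6. When does 2.6 work?** If EoBT precedes OL Day 1, its values pass the date test and are at most 14 days old. They are lost only if an item was left for OL Day 1.

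**The case against.** The best defence is that this is loose wording with little reach. The protocol does not fix the baseline visit on the first open-label dosing day; it permits it there, and an earlier EoBT is handled correctly. Laboratory by-visit tables and quality of life have rules that include the same day. SAP 5, in its own words, would admit a predose value. SAP 5 also promises only selected safety data for the open-label populations, so no text guarantees that ECG, ECOG or shift tables will be made for them. ECGs may be done when clinically indicated, which would shorten the ages above. A strict date rule also has a merit: it can never admit a post-dose value as baseline.

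All of that stands and limits the reach of the point, but the conflict remains. The two sentences in SAP 2.6 sit together; one refers to the dose and deals with same-day values, while the other refers to the date and does not. SAP 5 points back to 2.6 for the detail, so it cannot settle the matter.

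The last argument bears on the remedy. Extending the blinded convention would not be enough, because the protocol gives no time relative to dosing for vital signs, weight, ECOG or ECG on OL Day 1. Only quality of life is marked predose there, and laboratory results must be reviewed before dosing. Falling back on the protocol schedule would leave the exposed items unresolved.

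**Conclusion.** The point holds as an inconsistency in the SAP whose literal reading gives the wrong baseline for a subset of placebo crossovers. It matters only where a baseline assessment falls on OL Day 1, the item has no rule of its own, and 2.6 is followed as written. ECG is the most exposed, with a baseline 42 to 56 days old for progression at week 12 and 126 to 140 days at week 24 under the assumptions shown. How many patients this touches cannot be found from the documents.

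A reader might infer that every OL Day 1 value is lost, or that deterioration at progression will be charged to selinexor throughout the open-label safety tables. The documents do not support either. Several measures have same-day rules, the baseline visit may come earlier, and the set of open-label tables is not specified. Misattribution is possible wherever such summaries are produced, but it is not established. The affected outputs are descriptive; the PFS and OS analyses are untouched. This is a minor point that is worth correcting.

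**What to change.** Replace the open-label sentence in SAP 2.6 with: *the latest value before the first open-label dose, including EoBT Visit assessments and OL C1D1 assessments done in place of EoBT on OL Day 1; where the time on OL Day 1 is unknown, these baseline-visit assessments are treated as predose, and values recorded as after the dose are not baseline.* Use this one definition in Table 2-2, 4.2.2.2, 4.2.2.3 and section 5.

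The change is to SAP wording and needs no new data. The small cost is that an untimed OL Day 1 measurement actually made after the dose could occasionally be taken as baseline.

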2.7. VISIT WINDOWS

For safety data that are summarized/Plotted by time points, non-missing assessments from all scheduled and unscheduled visits will be mapped to an appropriate analysis visit using a windowing scheme. Analysis visit windows are defined in Table 2-1 to Table 2-2. If there are 2 or more assessments mapped to the same analysis visit for a patient, the assessment that is closest to the target visit day will be used for analysis. If there are 2 or more assessments mapped to the same analysis visit with the same distance from the target visit day, then select the latest one for the analysis.

Table 2-1 Visit Windows for Clinical Laboratory Tests for Patients in Blinded Treatment

Analysis Visit Name	Target Visit Day	Study Day Range in Window
Baseline	Day 1	Prior to or on Day 1
Day 43	Day 43	Day 2 to 64
Day 85	Day 85	Day 65 to 106
Day 127	Day 127	Day 107 to 148
Day 169	Day 169	Day 149 to 190
...		
(every 42 days)		

NOTE: Day 1 is the start date of blinded treatment period. The visit window is Target Date – 20 days to Target Date + 21 days for post-baseline visits, except Day 43 analysis visit.

Analysis visit and visit window may change for certain parameters depending on the data availability.

Table 2-2 Visit Windows for Clinical Laboratory Tests for Patients Who Enter Open-Label Treatment

Analysis Visit Name	Target Visit Day	Study Day Range in Window
OL Baseline	OL Day 1	Prior to or on OL Day 1
OL Day 43	OL Day 43	OL Day 2 to 64
OL Day 85	OL Day 85	OL Day 65 to 106
OL Day 127	OL Day 127	OL Day 107 to 148
OL Day 169	OL Day 169	OL Day 149 to 190
...		
(every 42 days)		

NOTE: Day 1 is the start date of open-label treatment period. The visit window is Target Date – 20 days to Target Date + 21 days for post-baseline visits, except OL Day 43 analysis visit. Analysis visit and visit window may change for certain parameters depending on the data availability.

2.8. SUBGROUPS

The following subgroup analyses on selected efficacy endpoints will be conducted for Phase 3 part:

- Prior eribulin use (prior eribulin vs. no prior eribulin).
- Prior trabectedin use (prior trabectedin vs. no prior trabectedin).
- Number of prior systemic therapies excluding eribulin and trabectedin (≤ 2 vs. ≥ 3).

